10.5 Safety Analyses

Adverse event data will be described and graded per the NCI CTCAE 5.0 guidelines. For each adverse event, information to be collected includes event description, time of onset, clinician assessment of severity, relationship to study product (assessed only by those with the training and

authority to make a diagnosis), and time of resolution/stabilization of the event. Regardless of relationship, all AEs will be recorded with start dates occurring any time after patient receives Y90 until 7 (for non-serious AEs) or 100 days (for SAEs) after the last day of study participation. At each study visit, the investigator will inquire about the occurrence of AE/SAEs since the last visit. Events will be followed for outcome information until resolution or stabilization.

Any medical condition that is present at the time that the participant is screened will be considered as baseline and not reported as an AE. However, if the study participant's condition deteriorates at any time during the study, it will be recorded as an AE. Changes in the severity of an AE will be documented to allow an assessment of the duration of the event at each level of severity to be performed. AEs characterized as intermittent require documentation of onset and duration of each episode.

The maximum grade for each type of toxicity will be recorded for each patient, and frequency tables will be reviewed to determine toxicity patterns. Adverse events will be summarized and described within each cohort. They will initially be reviewed regardless of attribution, but also whether they are possibly, probably, or definitely related to treatment. In addition, we will review all adverse event data that are graded as 3, 4, or 5 and classified as either "unrelated" or "unlikely to be related" to study treatment in the event of an actual relationship developing. The incidence of severe adverse events or toxicities will be described. We will assess the proportion of patients who experience grade 3 or higher non-hematologic toxicity. To assess tolerability, we will also capture the proportion of patients who go off treatment due to adverse events.

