4. STUDY DESIGN

4.1 Overall Design

This study is a single arm phase II prospective clinical trial in which patients with HCC who are deemed suitable for Y90 radioembolization will be recruited. Patients will undergo standard of care mapping study with ^{99}Tc -MAA to plan for Y90 radioembolization therapy. The additional, non-standard of care, intervention will be to do a second mapping study using low-dose Y90 (15 mCi) before the therapeutic Y90 radioembolization.

The distribution of MAA in terms of lung shunt fraction (LSF) and tumor to normal liver activity ration (TNR) will be compared to that of low-dose Y90. The treatment planning will be performed using standard of care MAA biodistribution using partition dosimetry model.

After administration of therapeutic Y90 dose, the actual dose delivered to tumor, non-tumoral liver (NTL) and lungs will be compared to the dose predicted by MAA and low-dose Y90.

The patients will be followed-up clinically and with imaging at 1, 3 and 6 months to determine tumor response, potential treatment related toxicity and to determine TDRT.

Hypothesis: Low dose Y90 microspheres as the treatment planning radiotracer will allow more accurate prediction of therapeutic Y90 liver biodistribution, which will enable us to perform prospective personalized dosimetry for every individual patient.

The results of this study will determine the safety and efficacy of using low dose Y90 as a direct surrogate for treatment planning to ensure delivering cytotoxic Y90 dose to the targeted tumor(s), while concomitantly minimizing liver and lung toxicity with more accurate prediction of therapeutic Y90 biodistribution. **Our long-term objective is to increase the likelihood of objective tumor response, prolonged progression-free survival (PFS) and overall survival (OS) in patients with HCC treated with Y90 RE.**

The study is a single-arm in study in which each patient will undergo two sets of mapping procedure before the actual Y90 therapy. One with standard of care ^{99}Tc -MAA and one with low-dose (15 mCi) Y90 microspheres. **Therefore, the additional intervention in the study is the second mapping procedure with low-dose Y90 microspheres.** Each patient will be used as their internal control to minimize selection biases. **Additional to standard of care Y90 SPECT/CT after therapy, the patient will undergo one PET/CT after low-dose Y90 and one PET/CT after Y90 therapy.**

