7.3.3 Rescue Medications & Supportive Care

Patients whose treatment is interrupted or permanently discontinued due to an adverse event or clinically significant laboratory value, must be followed up at least once a week (or more frequently if required by institutional practices, or if clinically indicated) for 4 weeks, and subsequently at approximately 4-week intervals, until resolution or stabilization of the event, whichever comes first. Appropriate clinical experts such as ophthalmologist, endocrinologist, dermatologist, psychiatrists etc. should be consulted as deemed necessary. All patients must be

followed up for adverse events and serious adverse events until start of new antineoplastic medication or 150 days after discontinuation of study drug, whichever is sooner. Suspected SAEs will continue to be collected beyond the 150-Day safety visit. This will be done by return clinic visits, laboratory checks, and phone calls. The emergence of Immune-Related AE (irAE) may be anticipated based on the mechanism of action of immunomodulatory therapies. Serologic, histologic (tumor sample) and immunological assessments should be performed as deemed appropriate by the Investigator to verify the immune-related nature of the AE and to exclude alternative explanations. Recommendations have been developed to assist investigators in assessing and managing the most frequently occurring irAEs.

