7.5 Duration of Follow Up

Patients will be followed for approximately 180 days after Y90 therapy according to the SoA's detailed above to determine both safety and efficacy. The patients will then be followed every 3 months as per standard of care at Emory IR. This will generally continue until patient's death, enrollment in hospice or loss to follow-up.

Long-term follow-up should continue until the patient's withdrawal of consent or loss to follow up, death, or study termination. In case of a clinically significant AE, patient will be followed for safety until resolution or permanent sequelae of all toxicities attributable to study drug(s). If the patient discontinues study drug for a clinically significant AE, the patient will be followed until resolution of the AE or the event is considered to be stable and/or chronic.

A participant will be considered lost to follow-up if he fails to return for three scheduled visits and is unable to be contacted by the study site staff after three attempts at contact by phone.

The following actions must be taken if a participant fails to return to the clinic for a required study visit:

- The site will attempt to contact the participant and reschedule the missed visit and counsel the participant on the importance of maintaining the assigned visit schedule and ascertain if the participant wishes to and/or should continue in the study.
- Before a participant is deemed lost to follow-up, the investigator or designee will make every effort to regain contact with the participant (where possible, 3 telephone calls and, if necessary, a certified letter to the participant's last known mailing address or local equivalent methods). These contact attempts should be documented in the participant's medical record or study file.
- Should the participant continue to be unreachable, he will be considered to have withdrawn from the study with a primary reason of lost to follow-up.

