11.5 Adverse Event and Serious Adverse Event Reporting

11.5.1 Adverse Event Reporting

From the time of treatment allocation through **90** days following cessation of treatment, all adverse events, that begin or worsen after informed consent, **must be recorded** by the investigator or designee at each examination on the Adverse Event case report forms/worksheets.

The investigator will make every attempt to follow all subjects with non-serious adverse events for outcome.

Conditions that were already present at the time of informed consent should be recorded in the Medical History page of the patient's CRF/worksheet.

Adverse events will be assessed and graded according to the Common Terminology Criteria for Adverse Events (CTCAE) version 5.0. Grade 1 to 5 will be used to characterize the severity of the Adverse Event.

If CTCAE grading does not exist for an adverse event, the severity of mild, moderate, severe, and life-threatening, death related to the AE corresponding respectively to Grades 1 - 5, will be used. Information about any deaths (related to an Adverse Event or not) will also be collected through a Death form (or EOT/SEC/Survival Information in NOVDD). The occurrence of adverse events should be sought by non-directive questioning of the patient (patient) during the screening process after signing informed consent and at each visit during the study. Adverse events also may be detected when they are volunteered by the patient (patient) during the screening process or between visits, or through physical examination, laboratory test, or other assessments. As far as possible, each adverse event should be evaluated to determine:

1. The severity grade (CTCAE Grade 1-5)
2. Its duration (Start and end dates)
3. Its relationship to the study treatment (Reasonable possibility that AE is related: No, Yes) or Its relationship to the study treatment (Reasonable possibility that AE is related: No, Yes, investigational treatment, Yes, the study treatment (non-investigational), Yes, both and/or indistinguishable)
4. Action taken with respect to study or investigational treatment (none, dose adjusted, temporarily interrupted, permanently discontinued, unknown, not applicable)
5. Whether medication or therapy was given (no concomitant medication/non-drug therapy, concomitant medication/non-drug therapy)

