For the time period beginning at treatment allocation through **90** days following cessation of treatment, or **180** days following cessation of treatment if the subject initiates new anticancer therapy, whichever is earlier, any serious adverse event, or follow up to a serious adverse event, including death due to any cause whether or not related to the study drug, must be **submitted on an SAE form** and assessed by PI in order to determine reporting criteria to regulatory authorities, IRB, DSMC, FDA or Sponsor.

All SAEs will be followed until satisfactory resolution or until the site investigator deems the event to be chronic or the adherence to be stable. Other supporting documentation of the event may be requested by the study sponsor and should be provided as soon as possible. The study sponsor will be responsible for notifying FDA of any unexpected fatal or life-threatening suspected adverse reaction as soon as possible but in no case later than 7 calendar days after the sponsor's initial receipt of the information.

All subjects with serious adverse events must be followed up for outcome.

Any additional information for the SAE including complications, progression of the initial SAE, and recurrent episodes must be reported as follow-up to the original episode **within 24 hours** of the investigator receiving the follow-up information.

An SAE occurring at a different time interval or otherwise considered completely unrelated to a previously reported one should be reported separately as a new event.

Any SAEs experienced after the reporting period described above should only be reported to FDA/IRB if the investigator suspects a causal relationship to the study treatment.

Information about all SAEs is collected and recorded on the **Serious Adverse Event Report Form**; all applicable sections of the form must be completed in order to provide a clinically thorough report. The investigator must assess and record the relationship of each SAE to each specific study treatment (if there is more than one study treatment), complete the SAE Report Form, and submit the completed form.

Each reoccurrence, complication, or progression of the original event should be reported as a follow-up to that event regardless of when it occurs. The follow-up information should describe whether the event has resolved or continues, if and how it was treated, whether the blind was broken or not, and whether the patient continued or withdrew from study participation.

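### Sections 7.3.3, 10.5 and 11.5 give three conflicting AE/SAE collection rules, so capture of late-onset non-serious toxicity and unrelated SAEs depends on which section the case report form follows

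*Combined protocol and SAP*

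**What the plan says.** Collection rules appear in four sections.

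- **Section 10.5** records all AEs, whatever their relationship, with onset after the patient receives Y90 and "until 7 (for non-serious AEs) or 100 days (for SAEs) after the last day of study participation". Section 10.1 refers the reader to 10.5 for the safety analysis plan.
- **Section 11.5.1** makes recording on the AE form obligatory from treatment allocation through 90 "days following cessation of treatment, all adverse events, that begin or worsen after informed consent".
- **Section 11.5.2** requires SAE forms through 90 days after treatment ends, or 180 "days following cessation of treatment if the subject initiates new anticancer therapy, whichever is earlier". After that, SAEs go to FDA/IRB only if a causal link is suspected.
- **Section 7.3.3** follows patients for AEs and SAEs "until start of new antineoplastic medication or 150 days after discontinuation of study drug, whichever is sooner", and adds: "Suspected SAEs will continue to be collected beyond the 150-Day safety visit". The Schedule of Activities (Section 1.3) has no 150-day visit.

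Safety follow-up is longer than some of these limits. Section 7.5 states: "Patients will be followed for approximately 180 days after Y90 therapy according to the SoA's detailed above to determine both safety and efficacy". Section 4.1 places visits at 1, 3 and 6 months, partly to determine treatment-related toxicity.

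**The concern.** Safety is part of the primary objective (Section 3), and all-grade Y90 toxicity is a secondary endpoint (Section 1.1). Section 10.5 promises the maximum grade of each toxicity per patient and the proportion of patients with grade 3 or higher non-hematologic toxicity. Both depend on the period in which a new event counts.

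The rules use different end points and different anchors: end of participation in 10.5, end of treatment in 11.5, and discontinuation of study drug or new medication in 7.3.3. The 6-month visit lies inside the 10.5 window and after the single-session limits in the other sections. If AE forms are built on 11.5.1, late events may be missing or captured unevenly when the 10.5 tables are made, and that is hard to repair afterwards.

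The starts also disagree. Section 10.5 opens after Y90, 11.5.1 at treatment allocation for events after consent, and Section 9.1 counts toxicity from the first Y90 therapy. The safety endpoint in Section 3 includes angiography-related events, and the MAA angiography comes before any Y90.

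**Working it through.** The plan gives no figure to reproduce. The check puts each rule on one time axis and counts how much of the second half of follow-up it covers.

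**Inputs**

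- Day 0 is the first therapeutic Y90.
- T is the day of the last Y90 therapy, which Section 8.1 takes as end of treatment. T = 0 for one session. T = 28 if the second session at 4 weeks in Section 7.4.1 is given.
- P is the last day of participation. I take P = 180, from the 6-month participant duration in Section 1.1 and the follow-up in Section 7.5. This is an assumption, since 10.5 does not define the term.
- N is the day new antineoplastic medication starts, if it does. N = 90 is used as an example, because Section 7.4 allows other therapies after progression at 3 months.

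**Formulas**

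- 10.5: P + 7 (non-serious) or P + 100 (SAE).
- 11.5.1: T + 90.
- 11.5.2 read literally: T + min(90, 180) = T + 90. If 180 days was meant after new therapy: T + 180.
- 7.3.3: the earlier of T + 150 and N.
- Days covered out of the 90 from day 91 to day 180: max(0, min(closing day, 180) − 90).

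**Results**

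| Rule | Closes, one session | Days 91–180 covered | Closes, second session at day 28 | Days 91–180 covered |
|---|---|---|---|---|
| 10.5, non-serious | 180 + 7 = 187 | 90 (100%) | 187 | 90 (100%) |
| 10.5, SAE | 180 + 100 = 280 | 90 (100%) | 280 | 90 (100%) |
| 11.5.1, all AEs | 0 + 90 = 90 | 0 (0%) | 28 + 90 = 118 | 28 (31%) |
| 11.5.2, SAE, literal | 0 + 90 = 90 | 0 (0%) | 118 | 28 (31%) |
| 11.5.2, SAE, 180-day reading | 180 | 90 (100%) | 28 + 180 = 208 | 90 (100%) |
| 7.3.3, no new medication | 0 + 150 = 150 | 60 (67%) | 28 + 150 = 178 | 88 (98%) |
| 7.3.3, new medication at day 90 | 90 | 0 (0%) | 90 | 0 (0%) |

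If participation after a second session ran to 28 + 180 = 208, 10.5 would close at 215 or 308, with the same coverage.

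**Another reading of participation.** Suppose its last day were the end-of-treatment visit, which Section 7.6 places 30 days after the last dose. For one session, 10.5 would close at 30 + 7 = 37 for non-serious AEs (0 of 90 days) and 30 + 100 = 130 for SAEs (40 of 90, or 44%). The sections would still disagree.

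**Example.** A new non-serious grade 3 event has onset on day 120 after a single session. Section 10.5 includes it. The recording duty in 11.5.1 has lapsed. Section 7.3.3 includes it only if no new antineoplastic medication has started.

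**Start.** Section 1.3 puts the MAA angiography at 7:30–9:30 AM and low-dose Y90 delivery at 11:30 AM–1:00 PM on the same Monday. A complication arising in the first angiography therefore starts before 10.5 opens, even if low-dose Y90 counts as receiving Y90.

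**The case against.** The strongest reply is that the plan already leads to full capture. Section 10.1 identifies 10.5 as the safety analysis plan, and 10.5 covers the whole of follow-up when participation runs to day 180. Sections 10.5 and 11.5.1 both call for AE inquiry at each visit, and the 6-month visit is a study visit. Section 13.2 has AEs recorded along the follow-up schedule and all grades of Y90-related AEs recorded, with no 90-day limit. Section 7.3.3 keeps suspected SAEs open, 11.5.2 keeps causally suspected SAEs reportable, and 7.5 follows clinically significant AEs to resolution or permanent sequelae.

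Much of this stands, and it rules out three stronger readings.

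- A reader might infer that an event found at the 6-month visit goes unrecorded under 11.5.1. That section sets a minimum period; it does not bar later recording, and it asks about AEs at each visit.
- A reader might infer that the toxicity rates are undefined. Section 10.5 gives a window, a grading scale and the summaries.
- A reader might count four incompatible windows. Sections 11.5.1 and 11.5.2 share a 90-day base and differ by event class, so there are three conflicting rules.

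The reply does not settle which section governs the case report form. Section 10.5 is named for analysis, 11.5.1 states what must go on the AE form, and no text ranks them. Follow-up to resolution applies to events already identified, not to new late ones.

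**Conclusion.** The contradiction is real and worth correcting, but its consequence is limited. It remained under every reading tried: one or two sessions, new medication at day 90, either reading of 11.5.2, and either meaning of last day of participation. For a single session with participation to day 180, coverage of days 91 to 180 ranges from 0% to 100% by section.

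The events mainly exposed are late-onset non-serious AEs, including grade 3 or higher toxicity that does not meet the seriousness definition, and SAEs judged unrelated. Angiography complications arising before any Y90 are exposed at the other end of the 10.5 window.

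The effect on a reported rate cannot be estimated, because the documents give no expected number of late events. One patient in 30 is 1/30 = 3.3 percentage points, which is the size of a single omission and not a forecast. Safety is summarised descriptively, so sample size and power are unaffected.

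**What to change.** Reconcile Sections 7.3.3, 10.5, 11.5.1 and 11.5.2 so that each states the same start, anchor and end for each event class.

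- **Start:** early enough to capture events from the first mapping angiography, with the Section 9.1 toxicity definition brought into line.
- **Anchor:** one defined date, stating how a second Y90 session affects it. If last day of participation is kept, define it.
- **End for non-serious AEs:** at least through the 6-month visit. Keep events that follow new anticancer therapy and flag them, so they can be shown separately.
- **End for SAEs:** no shorter than the 100-day tail in 10.5, with the collection of suspected SAEs in 7.3.3 kept. Ending SAE capture at the 6-month visit would make the sections agree but would discard safety data the plan now intends to collect.
- **Section 11.5.2:** correct the closing clause so that the 180-day branch can operate, or remove that branch.
- **Precedence:** state that the case report form follows the reconciled window.

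The cost is wording in these sections and slightly more AE recording. No visit is added, since visits already run to 6 months.

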10.5.1 Baseline descriptive statistics

The following baseline descriptive statistics will be performed:

1. Mean and Median Age and standard deviation
2. Frequency of Male vs. Female
3. Frequency of underlying cause of cirrhosis: Hepatitis B, Hepatitis C, Alcohol, NASH, others, no cirrhosis.
4. Mean and Median maximal tumor diameter for index tumor with standard deviation
5. Mean and Median number of lesions with standard deviation

10.5.2 Planned interim analyses (if applicable)

N/A

10.5.4 Analysis of secondary endpoints

Secondary clinical endpoints will be evaluated to assess outcomes including biology of resistance and survival. The endpoints with their definitions are listed as follows:

1. Tumor Dose Response Threshold (TDRT): defined as the Y90 dose that results in CR or PR
2. Tumors with LD 50 and LD 70: Defined at frequency of tumors in which 50% or more or 70% or more of their volume received above TDRT and their correlation with response.
3. Time to progression (TTP): defined as the time from start of protocol therapy until the criteria for disease progression are met. Patients who are either lost to follow-up, die or who begin alternative treatments prior to progression, will have their data censored as of the date considered to be lost to follow-up, date of death, or the first day of alternative therapy.
4. Progression-free survival (PFS): defined as the time from start of protocol therapy to disease progression or death from any cause, censoring patients without an event at time of last clinical assessment.
5. Overall survival (OS): defined as the time from start of protocol therapy to death, censoring patients who are alive at last follow-up

Protocol therapy related toxicities rate will be summarized using descriptive statistics such as frequencies and proportions. Differences in the proportion of patients who experience protocol-related toxicities will not be compared between cohorts.

To compare TDRT and Tumors with LD 50 and LD 70 between two groups, two sample paired t-tests will be conducted when data followed a normal distribution, otherwise Wilcoxon signed rank test will be used instead. General linear model (GLM) will be further used in the multivariable analysis to estimate the adjusted efficacy of treatment (MAA vs Y90) on TDRT and Tumors with LD 50 and LD 70 after adjusting for other factors, respectively. Pearson correlation coefficients will be calculated to measure the correlation between two numerical variables, and the significance of coefficients will be tested using Wald's test.

Time to event outcomes including TTP, PFS and OS will be evaluated using the methods of Kaplan and Meier, with a focus on graphical evaluation as well as early time-point and median estimates of survival distributions with 95% confidence intervals. The TTP, PFS and OS of each patient group at specific time points, such as 1 year, 3 years, and 5 years, etc. were also estimated alone with 95% CI. Cox proportional hazards models were further used in the multivariable analyses to assess adjusted effects of treatment (MAA vs Y90) on the patients' TTP, PFS and OS after

adjusting for other factors. The proportional hazards assumption was evaluated graphically and analytically with regression diagnostics. All data management and statistical analysis were conducted using SAS Version 9.4 (SAS Institute, Inc., Cary, North Carolina).

